8. OUTPUT PRESENTATIONS

Summary results will be presented separately by Stage 1 and Stage 2.

Efficacy analysis: For Stage 1, summary will be by dose level. For Stage 2, summary will be by type of malignancies.

Analysis other than efficacy: For Stage 1, summary will be by dose level and total. For Stage 2, summary will be by type of malignancies and total.

9. DISPOSITION AND WITHDRAWALS

All patients who provide informed consent will be accounted for in this study.

9.1. DISPOSITION

Patient disposition, discontinuation as well as reasons for discontinuation will be presented for the all enrolled set. The number of patients who provided the informed consent for the study will be summarized, Screen failed patients and the reason for screen failure will also be summarized.

The number and percentage of patients who received, discontinued or are still on the treatment will be presented. Reasons for discontinuation from study treatment as recorded on the "End of Treatment" form will be summarized. The number and percentage of patients who have discontinued or are still on study will be presented. Reasons for discontinuation from study as recorded on "End of Study" form will be summarized. The follow up time will be also summarized with mean, median, minimum, maximum and standard deviation.

Follow up time (months) = (date of death (if the subject died) or last known alive date (if the subject is not known to die) – the first dose date + 1)/30.4375. For the interim evaluation of Stage 1 results, follow-up time (days) is defined as date of cutoff (even if patient was off treatment or died) – first dose date +1.

In addition, number and percentage of patients with <6, >=6, <12, >=12 months follow-up time will be summarized

The number/percentage of patients included in FAS, EAS, and DEAS (stage 1 only) will be summarized based on FAS for both Stage 1 and Stage 2. A by-patient listing will include the inclusion/exclusion of patients in each analysis set.

Individual listings containing the site and subject ID, informed consent information, first and last non-zero study medication administration date, treatment discontinuation information and end of study information will be provided separately for Stage 1 and Stage 2. A separate data listing will include eligibility for study entry based on inclusion/exclusion criteria.

9.2. Protocol Deviations

Protocol deviation will be collected by clinical team and entered into clinical trial management system (CTMS).

A summary table for major protocol deviations by deviation category will be presented. A subject will only be counted once within a particular deviation category even if he/she has multiple deviations under the same category.

All protocol deviation will be presented in listings including deviation category, deviation term, deviation date, severity (major/minor), actions taken, COVID-19 impact related.

COVID-19 Visit Impact to planned visit will be included in by-patient listings.

10. DEMOGRAPHIC AND BASELINE CHARACTERISTICS

Demographics and other baseline characteristics will be presented for the FAS.

Protocol Number: 2018-689-00US1 Page 25 of 43

Continuous demographic variables: age, height at baseline, weight at baseline, and body mass index at baseline will be summarized using descriptive statistics (mean, standard deviation, median, minimum, and maximum). For all the other categorical variables, results will be presented as number and percentage of patients.

The following demographic and baseline characteristics will be reported for this study:

- Age (years) = floor (year of informed consent-year of birth)
- Age (years) category:
 - 0 < 65
 - o ≥65
- Gender (including childbearing potential for female patients)
- Race
- Ethnicity
- Weight at Baseline (kg)
- Height at Baseline (cm)
- BMI (kg/m2) at Baseline = weight(kg) /(height(m)*height(m))
- Tobacco Use Status
- Alcohol Use Status
- Drug Abuse Status
- Eastern Cooperative Oncology Group (ECOG) Performance Status at Baseline.
- B-symptoms (Present, Absent)
- Bone Marrow Involvement by Lymphoma

All above demographic information, cytogenetic abnormality test and bone marrow aspirate will be listed.

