Synopsis and Section 7.1 – Determination of Sample Size	Language was added to confirm the total expected enrollment is approximately 100 patients and approximately 100 patients are expected to enroll in the Dose Expansion Stage (Stage 2). Language associated with the change in expected enrollment was removed or updated for clarity.	The new language confirms the expected enrollment upon completion of enrollment upon implementation of this protocol amendment.
Synopsis, Section 3 – Objectives and Endpoints, Section 4.1.7 – Extended	Any language, headings, tables, and analyses related to assessments, objectives, and endpoints that fall	This language was updated or removed to clarify what assessments, objectives, and

Section Number	Summary of Change	Rationale for Change
Progression-Free Survival Follow-Up Period, Section 5.7 – Study Assessments, Section 5.8.2 – Extended Progression Free Survival Follow-up, Section 5.9 - Pharmacokinetic, Pharmacodynamic, and Pharmacogenetic Assessment Methods, Section 7 – Statistical Analysis, and Appendix 1, 2, 3, and 4.	outside of the scope of the necessary assessments for the safety review committee (SRC) to monitor the benefit/risk of patients remaining on trial were updated or removed.	endpoints are still relevant upon implementation of this protocol amendment.
Synopsis and Section 5.7.2 – Informed Consent Forms and Screening Log	Language regarding rescreening was updated to indicate that patients will not be rescreened upon implementation of Protocol Amendment 5.	This language was added to clarify that rescreening will no longer be permitted upon implementation of this protocol amendment.

EMERGENCY CONTACT

Under urgent circumstances, please contact the sponsor's medical monitor or the designee.

TABLE OF CONTENTS

TITLE PAGE	1
STATEMENT OF COMPLIANCE.....	2
SPONSOR’S APPROVAL.....	3
INVESTIGATOR’S AGREEMENT	4
DOCUMENT HISTORY	5
AMENDMENT SUMMARY	6
EMERGENCY CONTACT	8
TABLE OF CONTENTS.....	9
LIST OF ABBREVIATIONS.....	15
1 PROTOCOL SYNOPSIS	19
2 INTRODUCTION	29
2.1 Current Therapies and Unmet Medical Need	29
2.2 Background on HMPL-689.....	30
2.2.1 Preclinical Pharmacology	30
2.2.2 Preclinical Pharmacokinetics	30
2.2.3 Preclinical Toxicology	31
2.3 Clinical Experience of HMPL-689	33
2.4 Study Rationale and Benefit-Risk Assessment.....	35
3 OBJECTIVES AND ENDPOINTS	38
4 STUDY DESIGN.....	39
4.1 Overall Study Design.....	39
4.1.1 Dose Escalation Stage (Stage 1)	39
4.1.2 Dose Expansion Stage (Stage 2).....	43

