5.7.3 Medical History and Demographic Data

Medical history and demographic data will be collected at screening. The participant's consent gives the principal investigator, sponsor, sponsor's designees, and regulatory authorities, if applicable, direct access to obtain information from the patient's medical records, including electronic medical records, for the purpose of reviewing information about the participant's health

which is necessary as part of the implementation of the research project as well as for statutory control purposes, including self-regulation, quality control, and monitoring.

Medical history will include clinically significant diseases, surgeries, cancer history (including constitutional symptom/B-symptoms [Unexplained weight loss $\geq 10\%$ over previous 6 months, fever $>38^{\circ}\text{C}/100.5^{\circ}\text{F}$ for 2 or more weeks without other evidence of infection, night sweats for more than 1 month without evidence of infection]), prior cancer diagnosis (including tumor type, initial diagnosis date, immunohistochemistry, flow cytometry, other pathological findings), prior anti-neoplastic therapies and procedures and related outcome, use of tobacco, use of alcohol and drugs of abuse prior to the screening visit.

Demographic data will include date of birth, sex, and self-reported race/ethnicity.

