NCI-CTC National Cancer Institute Common Toxicity Criteria NCI CTCAE National Cancer Institute Common Terminology Criteria for Adverse Events NHL Non-Hodgkin Lymphoma nPR Nodular Partial Response ORR Objective Response Rate	MTD	Maximum Tolerated Dose
NCI CTCAE National Cancer Institute Common Terminology Criteria for Adverse Events NHL Non-Hodgkin Lymphoma nPR Nodular Partial Response ORR Objective Response Rate	MZL	Marginal Zone Lymphoma
Adverse Events NHL Non-Hodgkin Lymphoma nPR Nodular Partial Response ORR Objective Response Rate	NCI-CTC	National Cancer Institute Common Toxicity Criteria
nPR Nodular Partial Response ORR Objective Response Rate	NCI CTCAE	
ORR Objective Response Rate	NHL	Non-Hodgkin Lymphoma
•	nPR	Nodular Partial Response
PCFB Percentage Change from Baseline	ORR	Objective Response Rate
	PCFB	Percentage Change from Baseline

Protocol Number: 2018-689-00US1 Page 10 of 43

PDProgressive Disease PFS Progression Free Survival PK Pharmacokinetics PR Partial Response PR-L Partial Response with Lymphocytosis PT Preferred Term PTCL Peripheral T-cell Lymphoma QD Once Daily RP2D Recommended Phase 2 Dose SAP Statistical Analysis Plan SOC System Organ Class SDStable Disease SLLSmall Lymphocytic Lymphoma SRC Safety Review Committee TEAE Treatment-Emergent Adverse Event

TTR Time to Response

VGPR Very Good Partial Response WHO World Health Organization

WHO-DD World Health Organization Drug Dictionary

Note: Standard units such as mg and mL as used in the text are not included in the abbreviations list.

2. Introduction

This document describes the rules and conventions to be used in the presentation and analysis of efficacy and safety data for Protocol 2018-689-00US1. It describes the data to be summarized and analyzed, including specifics of the statistical analyses to be performed. The pharmacokinetics (PK) part will not be documented in this SAP and a separate analysis plan for PK analysis will be developed.

This statistical analysis plan (SAP) is based on protocol amendment 5 (dated 08Dec2022) and CRF version 6 (dated 13Jan2023).

Per protocol amendment 5, the end of the study is defined as 18 months after the last patient has been enrolled in the study or all patients have discontinued the study treatment, whichever comes earlier.

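### SAP section 10 derives age from calendar years alone, which overstates completed age by one year for every patient whose birthday falls after the consent date

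*SAP*

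**What the plan says.** SAP section 10 defines the variable as "Age (years) = floor (year of informed consent-year of birth" (closing bracket omitted here). The next item, "Age (years) category", has two levels, <65 and ≥65. The same section states that "Demographics and other baseline characteristics will be presented for the FAS", and that the demographic information is also listed.

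Protocol 5.7.3 says what is recorded at screening: "Demographic data will include date of birth, sex, and self-reported race/ethnicity". That is a date, not a year.

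Neither document gives another derivation of age or a reason for using years only. Other intervals in the SAP are built from full dates: follow-up time (9.1), time since diagnosis (11) and duration of exposure (15). The partial-date rules in SAP 7.10 cover adverse events, medications, death, last dose, diagnosis history and progression, but not date of birth.

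**The concern.** Age in a demographic table is ordinarily read as completed years at a stated date. The SAP formula does not produce that. It ignores month and day, so anyone who consents before reaching their birthday in that calendar year is given the age they will reach later in the year. The floor suggests that a difference of full dates was in mind, since flooring makes sense only for a fractional result. That is an inference; neither document says so.

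What is at stake is the accuracy of the reported ages and of the <65/≥65 split. The error runs in one direction, so it does not average out across patients. SAP section 8 presents non-efficacy summaries by dose level in Stage 1, SAP 7.9 uses the dose-level count as denominator, and the minimum cohort is 3 (SAP 4.2). In a column of 3, one misplaced patient changes the ≥65 share by 1/3, or 33 percentage points. The listing would also show an age that disagrees with one worked out from the date of birth.

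**Working it through.** The plan states no numerical result for age, so there is no figure to reproduce. The check compares the SAP rule with completed years.

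**Inputs.** The formula and the cut at 65 come from SAP section 10. Collection of date of birth comes from Protocol 5.7.3. The scale comes from the Amendment 5 summary in the Protocol: "total expected enrollment is approximately 100 patients". The spread of birthdays, the spread of consent dates and the age distribution are assumptions, because the documents give none of them.

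**Step 1: the difference between the two rules.** Completed age = (consent year − birth year) − 1 if the birthday falls after the consent date in that year, and − 0 otherwise. SAP age = consent year − birth year. So SAP age − completed age is either 0 or 1.

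Example: born 15 November 1956.
- Consent 1 March 2021: SAP age 2021 − 1956 = 65 (≥65); completed age 64 (<65).
- Consent 1 December 2021: both give 65.

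**Step 2: share of patients overstated.** With birthdays uniform over 365 days and consent on day d, the share is (365 − d)/365. Averaged over consent days:

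| Consent dates | Mean d | Share overstated |
|---|---|---|
| Even over the year | 183 | 182/365 = 49.9% |
| All in Q1 | 45.5 | 319.5/365 = 87.5% |
| All in Q2 | 136 | 229/365 = 62.7% |
| All in Q3 | 227.5 | 137.5/365 = 37.7% |
| All in Q4 | 319.5 | 45.5/365 = 12.5% |

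Each overstated patient is out by exactly one year, so the excess in mean age equals the share: about 0.50 year with even consent dates, and 0.125 to 0.875 year at the extremes. With 100 patients and a share of 50%, the 95% binomial range is 40 to 60 patients.

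**Step 3: the 65 cut.** Only patients aged 64 in completed years can change group, and only upward. A simulation of 2 million patients per scenario (normal ages, truncated below at 18, even consent dates) gave:

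| Mean, SD | Aged 64 | Of these, moved to ≥65 | Moved, of all patients |
|---|---|---|---|
| 60, 10 | 3.62% | 49.4% | 1.79% |
| 65, 10 | 3.99% | 49.9% | 1.99% |
| 68, 10 | 3.73% | 50.8% | 1.89% |
| 70, 8 | 3.96% | 51.0% | 2.02% |
| 65, 12 | 3.31% | 50.1% | 1.66% |

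None moved from ≥65 to <65. For 100 patients the expected number moved is 1.7 to 2.0. If patients are independent, the chance of at least one is 1 − 0.983^100 = 82% to 1 − 0.98^100 = 87%.

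**Step 4: where derived age is used.** It appears in the demographic summary and listing of SAP section 10. SAP 7.6 marks subgroups as not applicable. The efficacy definitions in SAP section 16 and the safety summaries in section 17 do not use it. The prognostic risk groups in SAP section 11 are read from CRF pages, not computed from this variable.

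**The case against.** The strongest reply is that a year-only rule may be deliberate. The SAP is written against "CRF version 6 (dated 13Jan2023" (SAP section 2), which is not available here, so the format of the birth field cannot be checked. Protocol 8.4 requires compliance with national privacy law, and some sites might record birth year only. What stands is that full dates cannot be assumed for every patient. The rest does not follow: Protocol 8.4 makes subject initials conditional on local rules but sets no such condition on date of birth, Protocol 5.7.3 names the date, and the SAP does not present the formula as a privacy fallback.

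It can also be said that neither document defines age as completed years. That is so. The formula departs from the ordinary meaning of age; it does not contradict a stated definition. The half-year excess is likewise measured against completed years. Those are themselves about half a year below exact decimal age on average, so the mean alone is a weak complaint. The 65 cut is not open to that reply: a patient who has not reached 65 is under 65 on either scale.

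A reader might go further and infer that the ages will clash with patient narratives or with the prognostic-index CRF pages. The documents do not support this. Neither describes narratives in the text available, and the CRF pages cannot be seen.

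**Conclusion.** The point holds as a small but definite error in a derivation rule. Followed literally, the formula adds a year for anyone consenting before their birthday in that year and never subtracts one. The direction follows from the formula; the size rests on assumptions. About half of patients affected, and a mean about 0.5 year above the mean of completed ages, require birthdays and consent dates spread evenly over the year. The figure of roughly 2 per 100 moved into ≥65 also requires the assumed age distributions. With around 100 patients spread over dose levels and malignancy types, most table columns would keep the same <65/≥65 split.

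A reader might infer that efficacy or safety conclusions are touched. They are not: derived age is descriptive, no endpoint or subgroup analysis uses it, and the study has no comparator arm. This is a correction worth making because it is cheap, not because a conclusion depends on it.

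**What to change.** Replace the line in SAP section 10 with age in completed years at informed consent, computed from the full dates of consent and birth: the year difference, less one if the birthday falls after the consent date in that year. Add a rule for partial birth dates: use the year difference only for patients whose CRF holds birth year alone, and footnote them in the table and listing. Before programming, confirm the birth-date field in CRF version 6.

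The cost is one line of SAP text with its footnote and one line of code. No new data need be collected for patients whose full date of birth is on the CRF.

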11. OTHER BASELINE DISEASE CHARACTERISTICS

Prior cancer diagnosis includes initial tumor type, immunohistochemistry, flow cytometry, other pathological findings.

FAS will be used to summarize baseline disease characteristics as following:

- Time since diagnosis (months): calculated as (date of first dose date date of primary diagnosis + 1)/30.4375
- Initial Tumor Type (CLL, SLL, MCL, FL, WM/LPL, MZL, PTCL, CBCL) and subtypes for FL, MZL, and PTCL, and prior BTK inhibitor exposure for MCL only.
- Risk Groups
 - For CLL/SLL/MZL: Low, Low-intermediate, High-Intermediate, High from "Diffuse Lymphoma International Prognostic Index" CRF page
 - For FL: Low, Intermediate, High from "Follicular Lymphoma International Prognostic Index" CRF page
 - For MCL: Low, Intermediate, High from "Simplified Mantel Cell

Lymphoma International Prognostic Index (MIPI) Score" CRF page

- For WM/LPL: Low, Intermediate, High from "International Prognostic Scoring System for Waldenstrom's Macroglobulinemia (ISSWM)" CRF page
- Rai stage (only for patients with lymphoma type CLL)
- Binet stage (only for patients with lymphoma type CLL)
- Ann Arbor Staging at study entry (for patients with lymphoma other than CLL)

All oncology diagnosis information and other baseline disease characteristics will be listed.

12. PRIOR ONCOLOGY THERAPY

Prior oncology therapy will be summarized for the FAS. Prior oncology therapies are defined as any anti-cancer therapy taken prior to initiation of study treatment. Prior oncology therapies include prior oncology chemotherapy and oncology medication, prior oncology radiotherapies and prior oncology surgeries/procedures.

Prior oncology surgeries/procedure

Prior oncology surgeries/procedures will be coded using MedDRA Version 26.0 or higher (depends on the latest data coding). Number and percentage of patients taken prior oncology surgeries / procedure will be summarized.

All prior oncology surgeries / procedure records will be listed with system organ class (SOC) and PT in the listing.

Prior oncology radiotherapy

Radiotherapies are not considered a line of prior oncology therapy. Radiotherapies will be summarized by numbers and percentages of patients taken radiotherapies, and all radiotherapy records will be listed.

Prior oncology chemotherapy and oncology medication

Prior oncology medication therapies will also be summarized as follows:

- Number and percentage of patients with at least one prior oncology medication therapy
- Number of previous lines of therapy
- Number and percentage of patients with 1, 2, 3, and >3 previous lines of therapy
- Time since last oncology medication therapy (month) = (date of first dose last date for the last therapy + 1)/30.4375
- Number and percentage of patients with Progression of Disease within 24 months

Protocol Number: 2018-689-00US1 Page 27 of 43

from the start of the first line of prior therapy (yes/no).

- Number and percentage of patients with any prior CD20 medication therapy
- Number and percentage of patients with any prior BTK inhibitor medication therapy

Prior oncology medications will be coded using World Health Organisation Drug Dictionary Enhanced (WHO-DDE) version MAR2023 or higher.

All prior oncology chemotherapy and oncology medication records will be listed with ATC level 2 text and preferred term (PT) in the listing.

13. MEDICAL HISTORY

Medical History information will be presented for the FAS.

All medical history from eCRF page 'Medical History' will be coded with Medical Dictionary for Regulatory Activities (MedDRA) central coding dictionary, Version 26.0 or higher.

All medical history records will be listed with system organ class (SOC) and preferred term (PT) in the listing.

14. PIOR AND CONCOMITANT MEDICATIONS AND PROCEDURES

14.1. PRIOR AND CONCOMITANT MEDICATIONS

Medications will be presented for the FAS and will be coded using WHO-DDE version MAR2023 or higher.

Refer to Section 7.10 for handling of missing or partial dates., In the case where it is not possible to define a medication as prior or concomitant based on dates, the medication will be classified as concomitant.

- 'Prior' medications are medications which started and stopped prior to the day of the first administration.
- 'Concomitant' medications are those which:
 - Started prior to the first administration date of study medication and ended on or after the first administration date on treatment.
 - Started on or after the first administration date of study medication but no later than 30 days following last administration date on treatment.

All prior and concomitant medication records will be listed with ATC level 2 text and PT in the listing.

14.2. Prior and Concomitant Procedures

Procedures will be presented for the FAS and will be coded using MedDRA Version 26.0 or higher.

- 'Prior' procedures are procedures which started and stopped prior to the day of the first administration.
- 'Concomitant' procedures are those which:
 - Started prior to the first administration date of study medication and ended on or after the first administration date on treatment.
 - Started on or after the first administration date of study medication but no later than 30 days following last administration date on treatment.

All prior and concomitant procedure records will be listed with system organ class (SOC) and preferred term (PT) in the listing.

14.3. Subsequent Medications and Non-drug Treatments

Subsequent oncology therapy is defined as any new anti-neoplastic therapy (including chemotherapy and medication, surgery/procedure, and radiotherapy) started after last dose of study medication. Medications will be coded using WHO-DDE version MAR2023 or higher. Procedures will be coded using MedDRA Version 26.0 or higher.

Subsequent oncology therapy will be listed for the FAS with ATC2 and PT in the listing for medications and with SOC and PT in the listing for surgery and procedures.

